Table 9	Product Descriptions	75

LIST OF FIGURES

Figure 1	Trial Design of Stage 1 (Adults)	14
Figure 2	Trial Design of Stage 2 Parts I and II (Infants).....	15

SUMMARY OF CHANGES

PRIMARY REASON(S) FOR THIS AMENDMENT:

Section Number (s)	Section Title(s)	Description of Change (s)	Rationale
6.0 7.1.2.1	Trial Flow Chart Physical Examinations	For the Infant Cohort, a full physical examination will be performed at Visit 1 and a targeted physical examination will be performed at all subsequent vaccination visits (Visits 2, 3, and 5). Physical examinations at these time points in the infant cohort are no longer optional, per investigator's discretion.	Revision
2.1 4.3 5.6	Trial Design Benefit/Risk Rescue Medications & Supportive Care	Include an additional criterion for rescue dose: pneumococcal IgG antibody, as measured by Pn ECL assay, below 0.35 µg/mL for serotype 19A.	New Addition

ADDITIONAL CHANGE(S) FOR THIS AMENDMENT:

Section Number (s)	Section Title (s)	Description of Change (s)	Rationale
4.1.3	Ongoing Clinical Trials	Added V114-006 as an ongoing clinical trial.	New Addition
5.1.2	Subject Inclusion Criteria	Infant Cohort, Inclusion Criterion #1: removed “if warranted” as physical examination is mandatory at Visit 1.	Clarification
8.6.1	Statistical Methods for Efficacy Analyses	Added a sentence clarifying that RCDCs will be included in the CSR.	Clarification
9.1	Investigational Product	Removed text related to clinical supplies for replacement subjects and other supplies.	Clarification
Overall	Overall	Minor editorial edits have been made in various sections throughout the protocol.	Revisions

1.0 TRIAL SUMMARY

Abbreviated Title	Safety/Immunogenicity of Different Formulations of V114
Sponsor Product Identifiers	V114
Trial Phase	I-II
Clinical Indication	Prevention of Pneumococcal Disease
Trial Type	Interventional
Type of control	Active Control
Route of administration	Intramuscular
Trial Blinding	Double-blind
Vaccination Groups	
Vaccine groups for V114 recipients are represented as V114 medium or V114 high as they respectively refer to the concentration of polysaccharide for each of the vaccine serotypes (1, 3, 4, 5, 6A, 6B, 7F, 9V, 14, 18C, 19A, 19F, 22F, 23F, and 33F) and Merck Aluminum Phosphate Adjuvant (MAPA). V114 medium contains capsular polysaccharides at 2μg/dose for all serotypes except 6B at 4μg/dose formulated with MAPA at 125μg/dose. In comparison, V114 high contains twice the amount of polysaccharide for each serotype (4μg/dose for all serotypes except 6B at 8μg/dose) and MAPA (250μg/dose).
 
The investigational 15-valent pneumococcal conjugate vaccine containing all 15 serotypes conjugated to the same carrier protein (CRM₁₉₇) will be simply referred to as V114 while the investigational 15-valent pneumococcal conjugate vaccine containing at least one serotype conjugated to an alternative carrier protein and the remaining serotypes conjugated to CRM₁₉₇ will be referred to as V114 with an alternative carrier protein.
 
Stage 1 - Adult Cohort:
 
Four (4) groups randomly assigned to receive a single dose of either V114 medium, V114 high, V114 medium with an alternative carrier protein, or V114 high with an alternative carrier protein.
 
Stage 2 - Infant Cohort:
 
Five (5) groups randomly assigned to receive either V114 medium, V114 high, V114 medium with an alternative carrier protein, V114 high with an alternative carrier protein, or Prevnar 13TM (control group). (See section 5.2 for a detailed description of the V114 formulation).

Number of trial subjects	Approximately 80 adult and 250 infant subjects will be enrolled.
Estimated duration of trial	The sponsor estimates that the trial will require approximately 21 months from the time the first subject signs the informed consent until the last subject's last visit.
Duration of Participation	
Stage 1 - Adult Cohort: Each subject will participate in the trial for approximately 30 days from the time the subject signs the Informed Consent Form (ICF) through the final contact. Each subject will receive a single dose of the study vaccine on Day 1. After vaccination, each subject will be followed for 14 days for adverse experiences (AEs). Serious AEs (SAEs) will be collected from the time the consent is signed through completion of the subject's participation in the study (i.e., 30 days postvaccination). Blood samples will be collected prior to vaccination and 30 days postvaccination.

	Stage 2 - Infant Cohort: Each subject will participate in the trial for approximately 11 to 14 months from the time the parent/legal guardian signs the ICF through the final contact. Each subject will receive 4 doses of the study vaccine given at 2, 4, 6, and 12 to 15 months of age. After each vaccination, the study subject will be followed for 14 days for AEs. SAEs will be collected from the time the consent form is signed through 30 days postdose 4 (PD4) and/or completion of the subject's participation in the study. Blood samples will be collected 30 days following the 3 rd dose, immediately prior to the 4 th dose, and 30 days following the 4 th dose.
Randomization Ratio	Stage 1 (adult cohort): 1:1:1:1 Stage 2 (infant cohort): 1:1:1:1:1

A list of abbreviations used in this document can be found in Section 12.5.

2.0 TRIAL DESIGN

2.1 Trial Design

This is a multicenter, randomized, double-blind (with in-house blinding procedures) study to evaluate the safety, tolerability, and immunogenicity of 4 different formulations of V114 in healthy adults and infants to be conducted in conformance with Good Clinical Practices (GCPs) at approximately 24 sites in the United States (US). Prevnar 13TM (pneumococcal 13-valent conjugate vaccine [diphtheria CRM₁₉₇ protein], Wyeth Pharmaceuticals, Inc., Philadelphia, Pa) will serve as an active control in the infant stage of the study. This study will enroll approximately 80 healthy adults 18 to 49 years of age (Stage 1) and 250 healthy infants 6 to 12 weeks (\geq 42 to \leq 90 days) of age (Stage 2). Prior to enrollment of infants, the safety and tolerability of a single-dose of the study vaccine must be demonstrated in healthy adults. Similarly, the safety and tolerability of the first dose of study vaccine must be demonstrated in a small cohort of infants prior to enrollment of the full infant cohort.

Stage 1 - Adult Cohort:

A total of 80 adult subjects will be randomly assigned to 1 of 4 formulations of V114:

- (1) Merck investigational V114 medium (N=20)
- (2) Merck investigational V114 high (N=20)
- (3) Merck investigational V114 medium with an alternative carrier protein (N=20)
- (4) Merck investigational V114 high with an alternative carrier protein (N=20)

The adult stage of this study is designed to evaluate the safety and tolerability of a single dose of 4 different formulations of V114 when administered intramuscularly to 80 healthy adults (20 per vaccination group).

Adverse events will be collected for 14 days following vaccination. After completion of a review of safety data from the adult cohort by an external Data Monitoring Committee (eDMC), Stage 2 of the study will begin.

Stage 2 - Infant Cohort:

Stage 2 will consist of 2 parts (Part I and Part II) during which a 0.5mL intramuscular dose of the study vaccine will be administered to healthy infants at 2, 4, 6, and 12 to 15 months of age. Each formulation of V114 will be first evaluated in a small number of infants (n=50) during Part I before initiating Part II which will enroll the remaining 200 infants. Prevnar 13TM will serve as control in both Part I and Part II.

Part I will involve 50 healthy infants (10 infants/group) who will be randomly assigned to receive 4 doses of 1 out of 4 different formulations of V114 or Prevnar 13TM. Safety data following the first dose [Postdose 1; (PD1)] will be reviewed by the eDMC prior to initiation of Part II. In Part II, an additional 200 healthy infants (40 infants/group) will be enrolled into the trial.

In Part I and Part II, infants will be given either:

- (1) V114 medium
- (2) V114 high
- (3) V114 medium with an alternative carrier protein
- (4) V114 high with an alternative carrier protein
- (5) Prevnar 13TM

(See Section 5.2 for a detailed description of the V114 formulations).

The safety and tolerability profiles of the different formulations of V114 and procedures within the clinical trial will be carefully monitored throughout the study by the SPONSOR in accordance with standard procedures and also by the eDMC. For this Phase I/II study, a Merck Research Laboratories (MRL) statistician and a MRL statistical programmer assigned to the protocol will be unblinded throughout the duration of the study to allow for timely review of the interim safety data by the eDMC. All personnel directly involved with the conduct of this trial will remain blinded to the subject's treatment assignment until medical/scientific review of all safety and immunogenicity data has been performed, protocol deviations have been identified, and data have been declared final and complete. Any study subject from Stage 2 (infant cohort) with serotype-specific anti-pneumococcal IgG (as measured by pneumococcal electrochemiluminescence [Pn ECL] assay) below 0.35 μ g/mL for serotype 19A (individually) and/or 4 or more serotypes in common with Prevnar 13TM at 1 month Postdose 3 (PD3) will be offered an additional dose of licensed pneumococcal conjugate vaccine outside of this protocol. See Section 5.6 Rescue Medications & Supportive Care for additional details of the rescue plan.

Specific procedures to be performed during the trial, as well as their prescribed times and associated visit windows, are outlined in the Trial Flow Chart - Section 6.0. Details of each procedure are provided in Section 7.0 – Trial Procedures.

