5.3 Randomization or Vaccine Allocation

Randomization will occur centrally using an interactive voice response system / integrated web response system (IVRS/IWRS). There are 4 V114 adult vaccination arms. Subjects will be assigned randomly in a 1:1:1:1 ratio to each of the 4 V114 vaccination groups in Stage 1, for the adult cohort. The infant cohort (Stage 2) will have 5 vaccination arms during which subjects will be randomly assigned in a 1:1:1:1:1 ratio to each of the 4 V114 vaccination groups or control (Prevnr 13™), respectively. Each formulation of V114 will be first evaluated in a small number of infants (10/arm) during Part I before initiating Part II, which will enroll the remainder of the infant cohort.

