5.4 Stratification

No stratification based on age, sex or other characteristics will be used in this trial.

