8.6 Statistical Methods

8.6.1 Statistical Methods for Efficacy Analyses

This section describes the statistical methods that address the primary and secondary objectives. Methods related to exploratory objectives will be described in the supplemental SAP.

Analysis of the immunogenicity data from the infant stage of the study will be based on the combined data from Stage 2 Part I and Stage 2 Part II.

To address the primary infant immunogenicity objective #2, GMCs at 1 month PD3 along with two-sided 95% CIs will be computed for the 15 serotypes in V114 for V114 medium, V114 high, and 13 serotypes in Prevnar 13TM. Point estimates of GMCs are the exponentiated estimates of the mean log_e concentrations. The confidence intervals for GMCs are the exponentiated confidence intervals for the mean log_e concentrations, based on 1-sample t-distributions. Additionally, GMC ratios (V114/Prevnar 13TM) along with two-sided 95% CIs will be computed for each of V114 medium and V114 high relative to Prevnar 13TM for the 13 common serotypes. The CI for the ratio will be calculated using a 2-sample t-test approach based on the natural logarithm of the ratio.

To address the secondary infant immunogenicity objective #1, the proportion of subjects achieving the serotype-specific threshold value of $\geq 0.35\mu\text{g}/\text{mL}$ for the 15 serotypes at 1 month PD3 along with the 95% CI will be calculated for V114 medium, V114 high, and the 13 serotypes in Prevnar 13TM. The one-sample two-sided CIs will be computed using the exact CI method for a single binomial proportion given in Collett [7]. Additionally, the

difference (V114 minus Prevnar 13TM) in the proportion of subjects achieving an IgG concentration $\geq 0.35\mu\text{g/mL}$ along with two-sided 95% CIs will be computed for each of V114 medium and V114 high relative to Prevnar 13TM for the 13 serotypes in common. The CI for the difference will be computed using the method of Miettinen and Nurminen [8].

The additional secondary infant immunogenicity objective (#2) as well as the secondary adult immunogenicity objective #1 will utilize similar statistical methods as those outlined above.

Reverse cumulative distribution functions for both IgG and OPA levels at PD3 and PD4 will be graphically displayed by serotype in the CSR.

Table 4 summarizes the key immunogenicity analyses.

Table 4 Analysis Strategy for Key Immunogenicity Variables

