8.7 Interim Analyses

Two interim analyses will be conducted during this study: (1) A first interim analysis will be performed when ~100% of the vaccinated subjects in the adult cohort and small infant cohort have completed postvaccination safety follow-up (single dose for adult cohort and postdose 3 for the small infant cohort) and ~100% of the immunogenicity results of IgG responses for adults (postvaccination) and small infant cohort (postdose 3) are available; (2) A second interim analysis will be performed in this study when ~100% of PD3 immunogenicity results for all infants in Stage 2 (small and large cohorts) are available. An internal statistician and statistical programmer assigned to the protocol will be unblinded throughout the duration of the study to facilitate the performing of the interim analysis as well as creation of the eDMC safety reports for ongoing safety review. Results of the interim analysis will be provided to the eDMC, and group summaries will be reviewed by the Sponsor's study team. The Sponsor's study team (except for the MRL statistician and programmer) will be blinded to the V114 formulation at the subject level. The Sponsor's study team will use the results to

make scientific decisions regarding future studies. It may also inform certain scientific consultations. No multiplicity adjustments will be made in either interim analysis as the conduct of the study will not be altered.

The endpoints, timing, and purpose of the interim analyses are summarized in [Table 6](#).

Table 6 Summary of Interim Analysis Strategy

Interim Analysis	Key Endpoints of Interim Analysis	Timing of Interim Analysis	Purpose of Interim Analysis

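### The primary PD3 GMC ratios pool infants from two separately allocated cohorts without a term for Part; the planned intervals are valid but slightly wider than needed, and a Part term is a nearly free improvement

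*Combined protocol and SAP*

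**What the plan says.** Section 2.1 sets up the infant stage as two cohorts. For the first, "Part I will involve 50 healthy infants (10 infants/group) who will be randomly assigned to receive 4 doses". After the eDMC has reviewed postdose 1 safety, "In Part II, an additional 200 healthy infants (40 infants/group) will be enrolled into the trial". The same five arms are listed for both Parts, and Prevnar 13 "will serve as control in both Part I and Part II". Section 5.3 gives one allocation ratio for the whole stage: "subjects will be randomly assigned in a 1:1:1:1:1 ratio to each of the 4 V114 vaccination groups or control". Section 5.4 names no stratum: "No stratification based on age, sex or other characteristics will be used in this trial".

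For the analysis, section 8.6.1 says that infant immunogenicity "will be based on the combined data from Stage 2 Part I and Stage 2 Part II". On the primary PD3 GMC ratio to Prevnar 13 it says: "The CI for the ratio will be calculated using a 2-sample t-test approach based on the natural logarithm of the ratio". Table 4 repeats this method for the per-protocol and FAS analyses, and gives an unstratified Miettinen and Nurminen interval for response-rate differences. Section 8.10 rules out analyses of baseline factors.

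On timing, the first interim analysis in section 8.7 takes place when the "immunogenicity results of IgG responses for adults (postvaccination) and small infant cohort (postdose 3) are available". The second waits for PD3 results from all infants.

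**The concern.** Because the number per arm is fixed within each Part, Part works as an allocation block even though section 5.4 names no stratum. Part I infants enrol earlier, perhaps at a different mix of sites. Their PD3 sera are also plausibly assayed in earlier runs, since the first interim needs their results. Sections 4.3 and 5.6 also need individual PD3 results before the end of the study. No section states how sera are batched, so separate assay runs are an inference.

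If GMCs differ between Parts for any of these reasons, a 2-sample t without Part counts that difference as residual variance. If the evaluable infants in two arms split differently between Parts, part of the difference also lands in the ratio for that pair of arms. At stake is the precision of the main immunogenicity output of an estimation study, which section 8.7 says will inform decisions on future studies.

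**Working it through.** **Inputs from the documents.** 10 and 40 infants per arm (2.1); 90% evaluability, so 45 per arm, taken as 9 from Part I and 36 from Part II; SD of ln IgG 1.0; 2-fold lower GMC; one-sided alpha 0.05 (8.9).

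**Input assumed.** The documents give no Part I/Part II difference. It is taken as 1.25-, 1.5- or 2-fold, common to all arms, with 3-fold as an extreme. The within-Part SD is 1.0.

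**Step 1: the plan's own figure.** The standard error of the log ratio is 1.0 × √(2/45) = 0.2108. The noncentrality is ln 2 / 0.2108 = 3.29. The noncentral t with 88 df gives a one-sided power of 94.71%, matching the stated 94.7%. The other cells of Table 7 also reproduce.

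**Step 2: residual variance when Part is ignored.** With d = ln(fold), the expected pooled variance within arm is 1 + (45/44) × 0.2 × 0.8 × d². The 95% CI factor (multiply and divide the ratio by it) is exp(1.987 × SD × 0.2108). With a Part term (87 df) it is 1.520.

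| Part difference | d | d² | Variance | SD | CI factor, no Part term | Excess log-scale width | Power at 2-fold |
|---|---|---|---|---|---|---|---|
| 1.25-fold | 0.223 | 0.050 | 1.008 | 1.004 | 1.523 | 0.4% | 94.6% |
| 1.5-fold | 0.405 | 0.164 | 1.027 | 1.013 | 1.529 | 1.3% | 94.2% |
| 2-fold | 0.693 | 0.480 | 1.079 | 1.039 | 1.545 | 3.9% | 93.3% |
| 3-fold | 1.099 | 1.207 | 1.198 | 1.094 | 1.582 | 9.4% | 90.9% |

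The power column is a little pessimistic. It treats the inflated SD as the sampling error of the ratio, whereas a Part difference shared by balanced arms cancels in the ratio and inflates only the estimated error. At 2-fold, the rejection limit is about 1.662 × 1.039 × 0.2108 = 0.364. The simulated SD of the log ratio is 0.2119, so (0.693 − 0.364)/0.2119 = 1.55, or about 94%.

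If the planning SD of 1.0 already contains Part variation, adding the term instead raises power from 94.7% to 94.9%, 95.2% or 96.0% (1.25-, 1.5-, 2-fold).

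**Step 3: bias and coverage.** In 20,000 simulated trials per scenario (10 + 40 per arm, 90% randomly evaluable), the mean error of the unstratified log ratio lay between −0.002 and +0.001 for 1.5-, 2- and 3-fold Part differences. Coverage of the unstratified 95% CI was 95.0%, 95.8% and 96.4%; with a Part term it was 94.7% to 94.9%.

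**Step 4: imbalance in one realised trial.** The ratio is multiplied by exp(difference in Part I share × d). With 10 versus 7 evaluable Part I infants and 36 from Part II in each arm, the difference in share is 10/46 − 7/43 = 0.0546. The multipliers are 1.012, 1.022 and 1.039 for 1.25-, 1.5- and 2-fold, and 1.062 at 3-fold. Under random 90% evaluability the SD of the difference in share is about 0.027, so this example is a roughly two-SD imbalance.

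**The case against.** The strongest reply is that nothing is wrong with the planned analysis. All arms share the same Part mix, each Part has its own Prevnar 13 group, and the unstratified interval covers at or slightly above 95%. Chance imbalance in Part share is random error that this interval already allows for, and 1% to 4% is small beside a CI factor of 1.52. The power statement of more than 90% survives every Part difference tried. Table 7 already spans SDs of 0.8 to 1.4, a far wider range than 1.000 to 1.039. Those SDs come from a multicenter trial of about 1,110 infants and may already include calendar, site and assay variation. Every assay run uses a reference standard curve and control sera (7.1.3.1), and Part II sera may themselves be spread over several runs, so Part may be a poor proxy for run. The first interim reports Part I separately, so a gross Part effect would not go unseen. All of this stands. It settles the priority of the point, but does not remove the small, avoidable loss.

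A reader might also infer that a formulation could stop after the Part I safety review, leaving an arm of Part I infants alone to be compared with a control group that is mostly Part II. The documents do not plan this. Section 2.1 fixes all five arms in both Parts, and sections 5.11 and 7.3.2 give guidance on halting or terminating the study as a whole. The oversight committee could in principle decide otherwise, but that would be a design change needing its own analysis plan.

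**Conclusion.** The point holds as a minor efficiency and robustness improvement, not as the correction of an invalid analysis. It would be wrong to read it as a claim that pooling shifts the GMC ratios systematically. A Part difference common to all arms cancels in expectation; only imbalance among evaluable infants moves a particular ratio, in either direction. If the vaccine effect itself differed by Part, the pooled ratio would be a 20/80 weighted average of the two effects on the log scale.

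The size depends entirely on an assumed Part difference. Up to 2-fold, the avoidable excess in log-scale CI width is at most about 4%, the power loss at most about 1.4 points (94.7% to 93.3%), and a two-SD imbalance moves a ratio by about 4% or less. Separate assay batching is plausible but not stated.

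**What to change.** In section 8.6.1 and Table 4, estimate each GMC ratio and its 95% CI from a linear model on log IgG with arm and Part (I/II) as factors, fitted to the two arms being compared. Keep the planned 2-sample t as a supportive analysis. Add a note that the model-based ratio may differ slightly from the quotient of the two reported GMCs when the evaluable Part split is unequal.

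Specify the change before unblinding, through an amendment or the supplemental SAP provided for in section 8.0. Preferably do so before the first interim, because group summaries then reach the study team.

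If response-rate differences are also stratified by Part with the Miettinen and Nurminen method, state the stratum weights (for example, sample-size weights), because Part I has only about 9 evaluable infants per arm.

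The cost is one degree of freedom (88 to 87) and a few lines of text. No new data and no change to allocation are needed.

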2.2 Trial Diagram

The trial design is depicted in [Figure 1](#) and [Figure 2](#)

[figure not shown]

Figure 1 Trial Design of Stage 1 (Adults)

[figure not shown]

Figure 2 Trial Design of Stage 2 Parts I and II (Infants)

3.0 OBJECTIVE(S) & HYPOTHESIS(ES)

3.1 Primary Objective(s) & Hypothesis(es)

No hypothesis testing will be performed.

For Stage 2 (Infants ONLY), the primary and secondary objectives in Section 3.0 will address the safety and immunogenicity (as measured by IgG) of 2 different formulations of V114 (medium and high as related to their contents in polysaccharide and adjuvant) containing the same carrier protein for all 15 serotypes in the vaccine, and Prevnar 13. The

exploratory objectives will address the safety and immunogenicity (as measured by IgG) of 2 additional formulations of V114 (medium and high as related to their contents in polysaccharide and adjuvant) containing an alternative carrier protein for at least one of the 15 serotypes in the vaccine, as well as the opsonophagocytic activity (OPA) from all vaccination groups (4 different formulations of V114 and Prevnar 13), as measured by multiplexed OPA [MOPA-4] assay.

Stage 1 - (Adults ONLY)

1. To evaluate the safety profile of a single dose of V114 with or without an alternative carrier protein.

Stage 2 - Parts I and II (Infants ONLY)

1. To evaluate the safety and tolerability profiles following receipt of each dose and across all doses of V114 medium, V114 high, and Prevnar 13™ when administered as a 4-dose regimen to healthy infants at 2, 4, 6, and 12 to 15 months of age.
2. To evaluate the serotype-specific IgG geometric mean concentrations (GMCs) of V114 medium, V114 high, and Prevnar 13™, and the IgG GMC ratios between each of these V114 formulations and Prevnar 13™ for the 13 common serotypes at 1 month postdose 3.

